After the patient leaves the BWH CCI, the study staff will randomize the patient to either the intervention (WGS+) or the comparison (WGS-) arm **[see attached randomization schema]**. The patient will remain blinded to the randomization until the results disclosure session. All blood samples will initially be sent to the Partners Laboratory for Molecular Medicine (LMM). Then, one tube of blood will be shipped to Illumina, Inc. for WGS and one tube of blood will be sent to the BWH Blood Bank for red blood cell antigen phenotyping. The LMM will retain one tube of blood for any necessary Sanger sequencing confirmation prior to reporting the results. If the patient is randomized to the comparison arm, both tubes of blood will be safely discarded.

Next the study staff will contact the participants to set up a time to complete the baseline qualitative interview **[see attached baseline qualitative interview guide – patients]**. All interviews will be conducted at the BWH CCI, be audio-recorded and will last approximately one hour. The audio-recordings will be de-identified, electronically stored on the MedSeq Project Manager computer and shared with the study investigators at Baylor College of Medicine and Duke University. Upon completion of the qualitative interview, the participant will receive \$40.

Once the physician has received the Genome Report and/or Family History Output, he or she will schedule the results disclosure session with the patient directly. The physician will alert the study staff of the appointment date and time. The physician will disclose the results to the patient. Patients in the Primary Care will either receive a Family History Output alone (comparison arm/WGS-) or a Family History Output and a Genome Report (intervention arm/WGS+) **[see attached randomization schema]**. The results disclosure session will take place in either the physician's clinic, office or the BWH

CCI. The results disclosure session will be audio-recorded. The audio-recordings will be de-identified, electronically stored on the MedSeq Project Manager computer and shared with the study investigators at Baylor College of Medicine and Duke University, which are both funded research subcontracts of this grant to analyze the audio-recordings generated from this project. During the results disclosure session, the physician will review the patient's family history with the patient for accuracies, gather additional information that the patient did not enter previously, and analyze, interpret and discuss the family history with the patient. The physician will make notes about the patient's family history and place the Output and their notes in the medical record. After the results disclosure visit, the physician will place the Genome Report and/or the Family History Report in the patient's medical record.

After the results disclosure session, the study staff will meet with the patient either at the BWH CCI or in the physician's clinic or office (space permitting) and administer the results disclosure survey **[see attached results disclosure survey]**. This survey will take approximately 30 minutes to complete. The study staff will immediately review the scales assessing depression and anxiety (The Hospital Anxiety and Depression Scale (HADS)). Should a patient score above our pre-specified cut-off scores for this scale, the study staff will alert the PI and the genetic counselor. The genetic counselor will call the patient after the visit, review the elevated score with the patient and ask questions to monitor the safety and well-being of the patient. The genetic counselor will document this conversation **[see attached Safety Monitoring Chart Note]**, and review the case with the PI. The PI and the genetic counselor will make appropriate referrals to the patient's primary care physician and/or a mental health professional as needed. All cases of safety monitoring will be reviewed by the IRB and the MedSeq Project Monitoring Committee according to our AE reporting protocol **[see attached AE reporting/MPMC schema]**.

At six-weeks and six months post-results disclosure, the study staff will contact the patient to set up a time to complete the follow-up surveys. The follow-up surveys will be administered either in person at the BWH CCI or by phone by the study staff. Each survey will take approximately 30 minutes to complete **[see attached six-week- and six-month follow-up surveys]**. Upon completion of the six-month follow-up survey, the patient will be given \$125.

After each six week- and six-month follow-up survey is complete, the study staff will immediately review the scales assessing depression and anxiety (The Hospital Anxiety and Depression Scale (HADS)). Should a patient score above our pre-specified cut-off score for this scale, the study staff will alert the PI and the genetic counselor. The genetic counselor will call the patient after the visit, review the elevated score with the patient and ask questions to monitor the safety and well-being of the patient. The genetic counselor will document this conversation **[see attached Safety Monitoring Chart Note]**, and review the case with the PI. The PI and the genetic counselor will make appropriate referrals to the patient's primary care physician and/or a mental health professional as needed. All cases of safety monitoring will be reviewed by the IRB and the MedSeq Project Monitoring Committee according to our AE reporting protocol **[see attached AE reporting/MPMC schema]**.

All subjects will be invited to participate in an additional qualitative survey at the six-month time point **[see attached 6-month qualitative interview guide – patients]**. Study staff will coordinate a time for the in-person or phone qualitative interview. All interviews will be conducted at the BWH CCI, be audio-recorded and will last approximately one hour. Patients who complete the qualitative interview will receive an additional \$40.

For any subject who withdraws from the study at any time, the study staff will complete a form documenting the reason for withdrawing from the study **[see attached patient withdrawal form]**.

Should a patient withdraw from the study prior to having their results disclosed to them by their physician, we will destroy the Genome Results report.

After all 6-month follow-up visits are complete, the study staff will review each patient's medical record to collect data regarding tests, procedures, referrals, etc. that have been initiated post-results disclosure. To conduct this medical record review, we will utilize the Partners Research Patient Data Registry (RPDR) as well as manual chart reviews.

Additional African American/African participants recruited in the extension phase of the study will all be placed in the whole genome sequencing arm of the study. They will undergo the same activities as the traditional MedSeq participants.

For Patients who we have identified to have a monogenic finding, that is a finding that could potentially impact their health risk, we plan to perform additional analysis. We will review their medical records looking, specifically with their variant in mind, to see if features associated with the variant were known prior to the study or were identified by further testing or by their physician during the course of the study. For individuals we feel may need further work-up we will contact them to offer them the option of coming in for additional phenotyping. If interested participants will sign the updated consent, which includes information about this visit and what will be included, **[see attached Physician Consent Form_Primary**

Care_extension 12.14.15]. If participants consent to participate, they will come in for a physical exam conducted by a clinical geneticist, [name] or [name] in the BWH CCI. They will have a more extensive family history collected by a certified genetic counselor and/or web-based program. We may also ask them to sign a release of medical records so that study staff can review medical records both within and outside the Partners Health Care System to determine if they have any known features associated with their genetic variant. The goal of this visit will be to determine if they have any previously undetected signs and symptoms of their genetic variant. We may also refer these participants for additional tests or imaging procedures relevant to their genetic variant. If associated features are identified follow-up recommendations will be made to the participant and their MedSeq provider in the form of a clinic note entered into the electronic medical record.

Cardiology

After the patient signs the consent form, the study staff will assign the patient a study ID number. Then, the study staff will administer the baseline survey **[see attached baseline survey]**. The baseline survey will be administered electronically using the computer in the room at the BWH CCI and will take approximately 30 minutes. The baseline survey will assess sociodemographics, genetic literacy, numeracy, personal health information, health behaviors, health intentions, health care utilization, insurance behaviors and intentions, shared decision making, general anxiety and depression, motivations for and perceived utility of WGS, preferences for receiving results, risk perceptions, biases and attitudes.

Once the baseline survey is completed, the study staff will immediately review the scales assessing depression and anxiety (The Hospital Anxiety and Depression Scale (HADS)). Should a patient score above our pre-specified cut-off scores for this scale, the patient will be excluded. The PI and the genetic counselor will speak to the patient by phone after this visit and make any appropriate referrals.

After the baseline survey is complete, the patient will complete a modified version of the online Surgeon General's "My Family Health Portrait" created for the MedSeq project by a company called 5AM Solutions, Inc. on the computer at the BWH CCI. This modified version of the Surgeon General's tool is identical to the Surgeon General's tool except that instead of asking for the patient's name, it will ask for the patient's MedSeq study number. Additionally, it allows the generated pedigree to be emailed in PDF format directly to the MedSeq Project Manager via a "submit" button. Like the online Surgeon General's tool, the modified version created by 5AM Solutions, Inc. temporarily stores the patient's family history information on servers outside of Partners and BCH only for the time needed for the, the patient's family history data is erased. Of note, the data that is temporarily stored on the 5AM Solutions servers does not contain any of the 18 HIPAA identifiers, and is thus, de-identified. The study staff will assist the patient in submitting his/her family history to the MedSeq Project Manager via the online program. Once the MedSeq Project Manager receives the family history in PDF, she will send it to the MedSeq study staff for distribution to the patient's physician prior to the patient's disclosure visit. **[see attached sample Family History Output]**.

In the baseline survey, we ask patients to list any non-prescription medications they are currently taking. The study staff will access the patient's medical record at the baseline visit to obtain and review with the patient the list of prescription medications they are currently taking **[see attached prescription medications checklist]**. For patients enrolled at BCH, medical records will be reviewed under the direction of [name] (co-PI of the MedSeq project and site-PI of MedSeq at BCH).

After the family history is complete, the phlebotomist at the BWH CCI will draw three tubes of blood on all participants. Participants will fill out a three-question survey for which responses will inform the blood typing and analysis with the sequencing data. **[see attached blood typing survey]**. After the blood is drawn, the first visit will be complete.

After the patient leaves the BWH CCI, the study staff will randomize the patient to either the intervention (WGS+) or the comparison (WGS-) arm **[see attached randomization schema]**. The patient will remain blinded to the randomization until the results disclosure session. All blood samples will initially be sent to the Partners Laboratory for Molecular Medicine (LMM). Then, one tube of blood will be shipped to Illumina, Inc. for WGS and one tube of blood will be sent to the BWH Blood Bank for red blood cell antigen phenotyping. The LMM will retain one tube of blood for any necessary Sanger sequencing confirmation prior to reporting the results. If the patient is randomized to the comparison arm, both tubes of blood will be safely discarded.

Next the study staff will contact the participants to set up a time to complete the baseline qualitative interview **[see attached baseline qualitative interview guide – patients]**. All interviews will be conducted at the BWH CCI, be audio-recorded and will last approximately one hour. The audio-recordings will be de-identified, electronically stored the MedSeq Project Manager computer and shared with the study investigators at Baylor College of Medicine and Duke University.

Upon completion of the qualitative interview, the participant will receive \$40.

Once the physician has received the Genome Report, the Targeted Cardiomyopathy Genetic Testing Report (if the patient has not yet learned their results) and/or Family History Output, he or she will schedule the results disclosure session with the patient directly. The physician will alert the study staff of the appointment date and time. The physician will disclose the results to the patient. Patients will receive a Family History Review with their physician and either a re-disclosure or new disclosure of their Targeted Cardiomyopathy Genetic Testing Report (comparison arm/WGS-) or they will receive a Family History Review with their physician, either a re-disclosure or new disclosure of their Targeted Cardiomyopathy Genetic Testing Report and a Genome Report (intervention arm/WGS+) **[see attached randomization schema]**. The results disclosure session will take place in either the physician's clinic, office or the BWH CCI. The results disclosure session will be audio-recorded. The audio-recordings will be de-identified, electronically stored on the MedSeq Project Manager's computer and shared with the study investigators at Baylor College of Medicine and Duke University. After the results disclosure visit, the physician will place the Genome Report and/or the Targeted Cardiomyopathy Genetic Testing Report and notes from the Family History Review in the patient's medical record.

After the results disclosure session, the study staff will meet with the patient either at the BWH CCI or in the physician's clinic or office (space permitting) and administer the results disclosure survey **[see attached results disclosure survey]**. This survey will take approximately 30 minutes to complete. The study staff will immediately review the scales assessing depression and anxiety (The Hospital Anxiety and Depression Scale (HADS)). Should a patient score above our pre-specified cut-off scores for this scale, the study staff will alert the PI and the genetic counselor. The genetic counselor will call the patient after the visit, review the elevated score with the patient and ask questions to monitor the safety and well-being of the patient. The genetic counselor will document this conversation **[see attached Safety Monitoring Chart Note]**, and review the case with the PI. The PI and the genetic counselor will make appropriate referrals to the patient's primary care physician and/or a mental health professional as needed. All cases of safety monitoring will be reviewed by the IRB and the MedSeq Project Monitoring Committee according to our AE reporting protocol **[see attached AE reporting/MPMC schema]**.

At six-weeks and six-months post-results disclosure, the study staff will contact the patient to set up a time to complete the follow-up surveys. The follow-up surveys will be administered in person at the BWH CCI by the study staff. Each survey will take approximately 30 minutes to complete **[see attached six-week- and six-month follow-up surveys]**. Upon completion of the six-month follow-up survey, the patient will be given \$125.

After the six week- and six-month follow-up surveys are complete, the study staff will immediately review the scales assessing depression and anxiety (The Hospital Anxiety and Depression Scale (HADS)). Should a patient score above our pre-specified cut-off scores for this scale, the study staff will alert the PI and the genetic counselor. The genetic counselor will call the patient after the visit, review the elevated score with the patient and ask questions to monitor the safety and well-being of the patient. The genetic counselor will document this conversation **[see attached Safety Monitoring Chart Note]**, and review the case with the PI. The PI and the genetic counselor will make appropriate referrals to the patient's primary care physician and/or a mental health professional as needed. All cases of safety monitoring will be reviewed by the IRB and the MedSeq Project Monitoring Committee according to our AE reporting protocol **[see attached AE reporting/MPMC schema]**.

All subjects will be invited to participate in an additional qualitative survey at the six-month time point **[see attached 6-month qualitative interview guide – patients]**. Study staff will coordinate a time for the in-person qualitative interview. All interviews will be conducted at the BWH CCI, be audio-recorded and will last approximately one hour. Patients who complete the qualitative interview will receive an additional \$40.

For any subject who withdraws from the study at any time, the study staff will complete a form documenting the reason for withdrawing from the study **[see attached withdrawal form]**.

Should a patient withdraw from the study prior to having their results disclosed to them by their physician, we will destroy the Genome Results report.

After all 6-month follow-up visits are complete, the study staff will review each patient's medical record to collect data regarding tests, procedures, referrals, etc. that have been initiated post-results disclosure. To conduct this medical record review, we will utilize the Partners Research Patient Data Registry (RPDR) as well as manual chart reviews. For patients enrolled at BCH, medical records will be reviewed under the direction of [name] (co-PI of the MedSeq project and site-PI of MedSeq at BCH).

We will keep audio and video recordings for 10 years after the completion of the study.

Optional GenomeConnect Validation Study:

Participants interested in the GenomeConnect validation study will visit a dedicated GenomeConnect URL (to track all participants referred from MedSeq). Potential participants will be instructed to register for an account at PatientCrossroads (the company hosting GenomeConnect). Following registration, the participant will be required to complete the GenomeConnect informed consent to enroll in the Geisinger IRB approved Genome Connect Study. After this they will be prompted to complete the body systems survey asking questions about his/her health as well as a brief survey to assess their socio-economic status [see **Body Systems Survey**]. They will then be prompted to complete the MedSeq validation study consent this will allow the release of their Body System Survey results from PatientCrossroads to MedSeq staff for validation purposes. They will next be prompted to fill out the **SES survey** [see **GenomeConnect MedSeq SES Survey**]. The self-reported Body System Survey data will be made available to MedSeq study staff for comparison with the participants' BWH medical record by MedSeq staff. Participation in GenomeConnect will continue unless the participant later chooses to end their participation, as described in the GenomeConnect consent and protocol.

The validation study will be conducted with collaborators at Geisinger Health System, who are enrolling their own participants. Only summary data from the MedSeq arm of the validation study will be shared with the Geisinger staff. No PHI will be exchanged between the two institutions [see **GenomeConnect MedSeq schema**].

Participants who complete the first consent and the Body Systems survey will be enrolled in the Geisinger approved GenomeConnect protocol. Participants who do not consent for both portions of the study will not be enrolled in the MedSeq validation study.

Optional MedSeq Project Long-Term Follow-Up

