The MedSeq Project study staff will distribute all Genome Reports and Family History Outputs to the physicians via Partners Secure File Transfer. Since the Genome Reports will take longer to generate than the Family History Outputs, the study staff will randomly match patients in the intervention (WGS+) and comparison (WGS-) arms within each study group. The MedSeq Project study staff will send these reports out at the same time. This will ensure that results disclosures in both the WGS+ and WGS- arms occur evenly over time throughout the duration of the study. Upon receiving the reports, the physician will have the opportunity to prepare for the results disclosure session, which includes consulting the Genetics Resource Center (GRC) as needed. If a physician consults the GRC, the GRC staff will document the encounter in the GRC logbook [see **attached GRC logbook**].

The study staff will keep track of all of the participant visits and when each patient's set of reports has been sent to the physician. The study staff will check in with the physicians periodically one week after receiving their patient's report(s) to coordinate a time to schedule the results disclosure visit. Once the physician deems his or herself adequately prepared for the results disclosure session with a particular patient, he or she will alert study staff. The study staff will coordinate a time for the physician and the patient to meet for the results disclosure session. The results disclosure visit will take place either in the physician's clinic, office or the BWH CCI. The results disclosure visit will be audio-recorded. The physician will give the audio recording to the study staff, and the audio-recordings will be de-identified, electronically stored on the MedSeq Project Manager computer and shared with the study investigators at Baylor College of Medicine and Duke University. After the disclosure, the LMM will send the Genome Report to the patient's medical record. Approximately one to two weeks after the results disclosure, the physician will complete a one-page post-disclosure visit checklist, which will take approximately 10 minutes to complete **[see attached post-disclosure MD checklist]**. The physician will document anything relevant to the patient's care as a result of this study in the patient's medical record.

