After the patient signs the consent form, the study staff will assign the patient a study ID number. Next, the study staff will administer the baseline survey **[see attached baseline survey]**. The baseline survey will be administered electronically using the computer in the room at the BWH CCI and will take approximately 30 minutes. The baseline survey will assess sociodemographics, genetic literacy, numeracy, personal health information, health behaviors, health intentions, health care utilization, insurance behaviors and intentions, shared decision making, general anxiety and depression, motivations for and perceived utility of WGS, preferences for receiving results, risk perceptions, biases and attitudes.

Once the baseline survey is completed, the study staff will immediately review the scales assessing depression and anxiety (The Hospital Anxiety and Depression Scale (HADS)). Should a patient score above our pre-specified cut-off scores for this scale (≥ 14 on anxiety subscale; ≥ 16 on depression subscale), the patient will be excluded. The PI and the genetic counselor will speak to the patient by phone after this visit and make any appropriate referrals.

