[name] at Duke University will oversee the coding of audio recordings using the ENCOUNTER software system. Once the coding of the disclosure conversations is completed, the relational database will be exported to Drs. [name] and [name] for analysis.

Drs. [name] and [name] will obtain IRB approval at their own institutions separately for their role in this project.

Quantitative Analyses

A statistician will lead quantitative analyses. Descriptive statistics will be used to characterize physicians and patients in terms of demographic variables, motivations for participating in this study, and disclosure preferences. Descriptive statistics will also be used to characterize patients in terms of genetic literacy and comprehension, the psychological impact and personal utility of testing, and response to the information in the following domains: (a) communication with family and/or other health care providers, (b) changes in insurance purchasing behaviors or intentions, and (c) changes in health behaviors, health care utilization or behavioral intentions (e.g., diet, exercise). For measures where we have both baseline and follow-up survey data we will use standard pre-post analyses (e.g., paired t-tests, repeated measures analyses) to assess whether significant changes occurred in these domains following receipt of test results.

An initial step in our quantitative data analytic plan will be to determine potential differences between the two groups of respondents coming from a primary care setting and a cardiology clinic. Given that those from the primary care clinic do not have any particular underlying condition for which a genetic test is being ordered (unlike the patients with cardiomyopathy), it will be important to determine whether patients from these two groups can be pooled across analyses or should be analyzed separately. We will therefore examine whether respondents from the two clinics differ at baseline on key demographic characteristics as well as on our main outcomes of interest (e.g., disclosure preferences).

Economic Analysis of Utilization Data

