Participants who choose to participate in the GenomeConnect validation study will receive a \$25 Amazon.com gift card. The gift card will be sent electronically to the email address used to register the participant for GenomeConnect, after the participant completes the body systems survey and the GenomeConnect MedSeq SES Survey.

Participants who choose to participate in the MedSeq Project Long-Term Follow-Up will receive a \$100 check.

Lottery for WGS

Participants who have been randomized to the comparison (WGS-) arm will have the opportunity to enter a lottery to receive WGS at the end of their study participation. Participants will be told about the lottery at their disclosure visit (visit 3) by the study staff. Following the disclosure visit with their physicians, study staff will ask participants if they would like to opt into the lottery for WGS. Study staff will remind participants that the lottery is completely voluntary. A total of three WGS will be reported through this lottery.

A drawing of those who have opted into the lottery will take place following the disclosure visit (visit 3) for the 33rd, 66th and 100th participants in the comparison (WGS-) arm. Winners of the lottery will be informed at their 6-month follow up visit (visit 5). At this time they can schedule a blood draw with the lab to be sent in for whole genome sequencing. Results will be reported through their own physician who is also a MedSeq Project enrolled physician. The GRC will be made available for any questions or concerns. If for any reason the patient's physician is unwilling or unable to report WGS results the study physician, [name], will report the WGS results to the participant at the BWH Center for Clinical Investigation or in the BWH Adult Medical Genetics Clinic. We will not survey or interview patients who received WGS as part of the lottery, however, we will apply the same data-sharing protocol as outlined above and include these patients in the medical record review. It is up to the physician's discretion to document any clinically relevant information learned as a result of this WGS report in the patient's medical record.

Physician Compensation

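### In primary care, follow-up surveys may move from the clinic computer to the phone, and the planned pre-post tests cannot separate that mode change from a change after results

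*Combined protocol and SAP*

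**What the plan says.** Section V (Study Procedures, Patients, Primary Care) opens the survey sequence with "Next, the study staff will administer the baseline survey" and adds: "The baseline survey will be administered electronically using the computer in the room at the BWH CCI". Randomization comes only after that visit. For the six-week and six-month surveys the same section says: "The follow-up surveys will be administered either in person at the BWH CCI or by phone by the study staff". It does not say who decides between the two, whether the in-person version is again on the computer, or whether the mode is noted.

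The Cardiology part of Section V has the same computer-based baseline but allows no phone survey: "The follow-up surveys will be administered in person at the BWH CCI by the study staff".

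In Section VI (Quantitative Analyses), measures with both baseline and follow-up data are to be analysed with paired t-tests or repeated measures methods "to assess whether significant changes occurred in these domains following receipt of test results". No term for survey mode is mentioned. Section VI also calls the aims predominantly exploratory, disclaims power for cross-group comparisons, and says differences across all study groups will be explored anyway.

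On knowledge of the arm, after the baseline visit "the study staff will randomize the patient to either the intervention (WGS+) or the comparison (WGS-) arm". Section V also states: "The MedSeq Project study staff will distribute all Genome Reports and Family History Outputs to the physicians via Partners Secure File Transfer". For the lottery, which is open only to the comparison arm, the plan says: "Participants will be told about the lottery at their disclosure visit (visit 3) by the study staff". Only patients are described as blinded, and only until disclosure.

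**The concern.** A paired test attributes to the intervening event everything that differs systematically between the two measurements. For a primary care patient surveyed by phone, two things differ: the patient has received results, and the survey has moved from a screen at the study centre to a phone conversation. The test sees only their sum.

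The baseline survey covers anxiety and depression, health behaviours, and insurance behaviours and intentions. On items like these, people may plausibly answer differently aloud to another person than on a screen. If distress is under-reported by phone, the pre-post test could show a fall that did not happen or hide a real rise. If healthy behaviour is over-reported, it could show an improvement that did not happen.

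The within-patient tests matter because the plan itself says it lacks the power for valid comparisons between groups. They also lack the protection that a contrast between arms offers against a shift common to everyone. If mode is not recorded when the survey is taken, no later analysis can recover it.

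**Working it through.** **Step 1. Where the documents establish a mode change.**

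| Survey | Primary care | Cardiology |
|---|---|---|
| Baseline | Study staff, on the centre's computer | Study staff, on the centre's computer |
| Six weeks, six months | Study staff, in person or by phone | Study staff, in person |

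A patient on the phone is not at the centre's computer, and no web link is offered for these surveys. The phone surveys therefore differ in mode from baseline. For in-person follow-up the text is silent, so no change is established there.

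**Step 2. Inputs for an illustration.** The documents state no alpha, standard deviation, correlation, mode effect or phone share, so there is no figure of the plan's own to reproduce. The Specific Aims give 100 primary care patients. I take 50 per arm, which fits the 50 primary care patients offered the GenomeConnect study, itself limited to the sequencing arm. All other inputs are assumptions: two-sided alpha 0.05, no true change, pre-post correlation r of 0.5 or 0.7, mode shift m of 0.1 to 0.3 SD, and phone share q of 25%, 50% or 100%.

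**Step 3. Formulas, in units of the outcome's SD.**

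- Mean bias in the paired difference = m × q.
- SD of the paired difference = √(2(1 − r)).
- Standard error = √(2(1 − r)/n).
- False-positive rate = probability that a noncentral t with n − 1 degrees of freedom and noncentrality (m × q)/SE falls outside the two-sided 5% limits.

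Example with n = 100, r = 0.7, m = 0.2, q = 0.5: bias = 0.10; SE = √(0.6/100) = 0.077; noncentrality = 0.10/0.0775 = 1.29; rate = 24.8%.

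Example with n = 50, r = 0.5 and the same m and q: SE = √(1/50) = 0.141; noncentrality = 0.71; rate = 10.7%.

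The formula ignores the extra variance from mixing modes, m²q(1 − q). This is at most 0.09 × 0.25 = 0.0225, against a paired variance of 0.6 to 1.0.

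**Step 4. Results (false-positive rate; 5% if no survey is by phone).**

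| n | r | m (SD) | 25% phone | 50% phone | 100% phone |
|---|---|---|---|---|---|
| 50 | 0.5 | 0.1 | 5.3% | 6.4% | 10.7% |
| 50 | 0.5 | 0.2 | 6.4% | 10.7% | 28.4% |
| 50 | 0.7 | 0.2 | 7.3% | 14.6% | 43.3% |
| 100 | 0.5 | 0.2 | 7.9% | 16.8% | 50.8% |
| 100 | 0.7 | 0.2 | 9.8% | 24.8% | 72.5% |
| 100 | 0.7 | 0.3 | 16.0% | 48.3% | 97.0% |

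The first and last rows are the extremes of the grid.

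**Step 5. The contrast between arms.** The bias in the WGS+ versus WGS- difference in change is m × (difference in phone share between arms). With equal shares it is zero. With a gap of 20 percentage points and m = 0.2 it is 0.2 × 0.2 = 0.04 SD.

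**The case against.** Several stronger readings are tempting, and the documents do not support them.

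- *All follow-up is in a new mode.* A reader might set a computer baseline against a staff-given follow-up throughout. But in-person follow-up takes place at the same centre and may use the same computer, and this covers all of cardiology. The survey instruments are attachments not available here and might settle it. The survey straight after disclosure is also in person, so one post-results HADS measurement never involves the phone.
- *The interviewer changes.* Study staff administer the baseline survey too. What changes is that nobody can know the arm at baseline, because randomization comes later, whereas staff can know it at follow-up.
- *Each follow-up survey is given by someone who knows the arm.* Randomizing, distributing reports and offering the lottery show this for the staff as a group, not for the person giving a particular survey. Patients also know their own arm by then, so their answers are unblinded whoever asks.
- *The comparison of arms is biased.* Nothing ties phone use to arm, and a shift common to both arms cancels.
- *The error rate is 72%.* That needs every follow-up survey to be by phone, with r = 0.7, n = 100 and a 0.2 SD shift. With a quarter by phone and a small shift, the rate stays close to nominal.

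It is also fair to say that the trial is exploratory, that no decision is tied to these tests, and that phone follow-up plausibly helps retention in a plan that enrols 300 to secure 200 completers. These points lower the stakes and argue for keeping the phone option. They do not explain why the mode is left uncontrolled in the plan.

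**Conclusion.** The point holds for primary care surveys taken by phone. For these, the pre-post tests mix any change after results with a move from computer to phone, and the protocol text provides neither for recording the mode nor for adjusting for it. By that time the staff giving the surveys belong to a group that can know the arm.

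The size is unknown. Over the assumed grid (no true change, two-sided alpha 0.05, n = 50 to 100, r = 0.5 to 0.7, shift 0.1 to 0.3 SD), the false-positive rate is about 5-16% with 25% by phone, 6-48% with 50% and 11-97% with all by phone. The effect may be negligible or dominant, depending mainly on a phone share that the plan leaves open. The WGS+ versus WGS- contrast is touched only if phone use or staff influence differs by arm. For an exploratory trial this is an inexpensive improvement worth making, not a flaw that invalidates the design.

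**What to change.** In the primary care follow-up paragraph of Section V, specify that in-person surveys at six weeks and six months use the same electronic form as baseline, and that patients who cannot attend are offered the form by secure web link. Keep the phone survey as a fallback. Require the mode of every survey to be recorded.

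In Quantitative Analyses, report the pre-post results with and without phone surveys. Patients who choose the phone may differ from the others, so this is a sensitivity analysis and not a full correction.

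The cost is modest. A web version of these surveys has to be set up: REDCap appears elsewhere in the protocol, but the patient web survey described there belongs to the separate five-year follow-up. Staff must also be on hand to review the HADS promptly when a form is submitted remotely, so that the review the protocol already requires is kept. Retention is protected because the phone stays available.
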